However, the core ACT clinical protocol does not contemplate providing the data summary and ML-prediction information to the receiving provider in the PACU or surgical wards. The proposed Outcome predictions, Data summaries, and Interpretive Notes Report (ODIN-Pilot) study will provide a "report card" containing automatically generated summaries of pre- and intraoperative data along with ML output. This information will be presented to multiple postoperative providers with different contexts and use cases. PACU physicians and registered nurses (RNs) receive handoff from the intraoperative team and assume care for the patient in the immediate postoperative phase (typically 45 minutes to several hours). They observe for appropriate recovery from anesthesia, surveil for developing complications, treat common side effects of anesthesia. When the patient is ready to leave the PACU and communicate their findings to the wards (surgical inpatient unit) RN. The PACU team also communicates to the intraoperative surgical team, who communicates to the wards "midlevel" (advanced practice nurse or resident MD) responsible for routine medical oversight, modifying medication strategies, and ordering additional diagnostic studies if necessary.

We hypothesize several mechanisms by which this ML report card may improve patient outcomes. First, the report card will function as an "alert" for patients at high risk and direct attention to them. This additional review may reduce postoperative complications. Second, the report card may frame handoff communications around important data and issues relevant to the patient. By focusing the postoperative provider on potential problems, it may improve anticipatory guidance between the intraoperative, supervisory, and frontline team members.

This pilot study will not focus on patient outcomes, but will attempt to measure these potential mechanisms. We will survey postoperative providers to measure perceived handoff quality and coverage of important topics. We will validate these surveys with direct observations, debriefing interviews, and structured handoff evaluation tools.

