### 4.2 Participants and Eligibility

#### 4.2.1 Inclusion criteria

• Adults undergoing OR procedures in BJH South campus, including all of "Pod 2", "Pod

- 3", "Pod 5" and excluding all procedure suites such as Interventional Radiology, Parkview Tower "Pod 1", Center for Advanced Medicine "Pod 4", Labor and Delivery suites.
- Surgical service is "Acute and Critical Care Surgery", Otolaryngology, Hepato-biliary, Vascular, or Abdominal Transplant
- Planned non-ICU disposition ("floor" and "observation unit" collectively "ward" patients).
- Calculated risk of unplanned ICU admission in the first 7 postoperative days in the top 15% of historical records.

Risk of unplanned ICU admission will use the same calculator currently employed in the ACT. Risk factors considered include the surgery performed, demographics, laboratory values, comorbidities, vital signs, and medications.

Although patients are exposed to effects of the intervention, data is obtained from healthcare providers. Included providers are PACU nurses, PACU anesthesiology physicians, wards nurses, and wards midlevel providers (resident physicians, physician assistants, and advanced practice nurses) who are involved in a postoperative handoff for these patients.

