#### Methods note

Risks generated using pre-anesthesia assessment, major comorbidities, laboratory values, and preoperative vital signs; errors in these values can significantly affect the calculations. Risk calculations use gradient boosted decision trees trained on BJH inpatient data 2019-2021. see https://pubmed.ncbi.nlm.nih.gov/31558311/

study ID 86915c307cbd5e01531052a04ff901d94371e8bf

The ACT detects that cases are near completion and that a report card should be triggered in two ways. First, the circulating nurse in each room electronically marks that a room is "close" in the EHR, usually during closure, to ensure that subsequent patients are called to the preoperative area and supplies for the next case are readied. This is performed with high fidelity as it is considered important to prevent case delays. The displayed OR schedule in Epic changes color, making this easily recognized. Second, an algorithm detects when changes in the anesthesia record suggest that the case is concluding. Both of these features cause the ML dashboard in the ACT (Figure 5) to highlight the patient as needing review to validate the report card. After manual validation, the report card will print directly in the operating room and a notification is sent to the circulating nurse to add it to the chart and provide it to the anesthesia team for handoff. The risk profile is then made active in a Best Practice Advisory in Epic.

-	nesthesia Control Tower ML Dash eview." Additional columns not sho			formation reda	acted. Yello	w highli	ght implies
Room Name	Description	akigr1\$	cardiac \$	death_in_3d=	DVT_PE\$	ICU \$	post_dialysis
BJH OR POD 2 ROOM 209	###LAPAROSCOPIC CHOLECYSTECTOMY	2.90%	1.60%	0.10%	8.80%	5.20%	0.10%
BJH OR POD 3 ROOM 301	EXPLORATION LIVER TRANSPLANT WITH WASHOUT LIVER BIOPSY AND BILE DUCT REVISION	67.10%	6.90%	7.60%	1.20%	93.40%	0.90%
BJH OR POD 2 ROOM 211	TRACHEOSTOMY PERCUTANEOUS	40.30%	2.70%	3.50%	7.40%	94.50%	0.20%

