#### 4.3.5 Adherence

Crossover from non-contact to contact will not occur because report cards are not generated for these patients. Our outcome survey will detect if providers believe they used the report, but no other encouragement to use it will be provided. Cross-over into non-contact (failing to contact the correct provider) will be minimized by appropriate training to ACT clinicians.

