#### 4.4 Outcomes

# **4.4.1 Primary Outcome Measures**

The primary outcome will be self-reported handoff effectiveness.

The following survey questions will be asked of postoperative providers:

Did you receive at handoff all the information you needed to safely take care of this patient?

[Yes, No]

Did you receive information from the team giving handoff to explicitly help you manage any potential complications or problems? [Yes, No]

If so, please list what problems / topics were discussed? [Free response]

[If with-intervention phase \* ] Did you look at or discuss the postoperative report card for this patient? [Yes, No]

[If  $^*$  yes] Did the report card contain any information that was notably misleading or incorrect?

[Yes, No]

[If yes, please describe: text box]

[If \* yes] Are there any important pieces of information that the computer should have included in the report card but didn't?

[Yes, No]

[If yes, please describe: text box]

[If \* yes] How much did the ML report change questions asked or information transfer at handoff?

[ Not applicable , Not at all , a little , a fair amount , a great amount ]

[If \* yes] How much effort was accessing the report card? [Very easy, easy, some effort, hard, unable to get to it or had to ask for help]

[If \* yes] Was the information presentation in the report card easy to understand? [Easy, some effort, hard to understand, unable to use or had to ask for help]

[If \* yes] Was the information in the report card relevant?
[a great amount, a fair amount, modestly, mostly not, not at all, not sure]

[If \* yes] Was the information in the report card useful to decision making or helpful to your understanding of the patient?
[a great amount, a fair amount, modestly, mostly not, not at all, not sure]

The following questions will additionally be asked of PACU resident physicians:

Did you participate in handoff for this patient? [Yes, No]

Did you visit this patient's bedside or speak to their nurse before being asked to sign them out? [Yes, No]

Figure 7 illustrates the RedCAP survey for safety questions which will be included throughout the study.

Figure 7: RedCAP Safety Survey

Postoperative Al Risk Report Card	Resize font:  Returning?

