#### **5.3 Statistical Methods**

Differences in the rate of acceptable handoffs will be compared with chi-square contingency table tests.

Although the primary analysis is intention to treat (comparing the with- and without-intervention groups directly), we will report as exploratory analyses per-protocol analyses in which patients whose report card was never accessed (outside of the ACT) are excluded.

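### Does the exploratory per-protocol analysis fail because section 5.3 does not say which record shows that a report card was accessed?

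*Combined protocol and SAP*

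**What the plan says.** Section 5.3 (Statistical Methods) makes the direct comparison of with- and without-intervention groups primary. It adds, as exploratory, "per-protocol analyses in which patients whose report card was never accessed (outside of the ACT) are excluded". It gives no data source, no list of people whose access counts and no time limit.

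The delivery route is in section 4.3.1, after the sample card. Printing takes place in the operating room once the card has been validated. The step that follows is described thus: "a notification is sent to the circulating nurse to add it to the chart and provide it to the anesthesia team for handoff". Next, "The risk profile is then made active in a Best Practice Advisory in Epic". Paper therefore comes before the electronic version.

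Two records could show access:

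- Section 4.3.3 says access is logged by IP address. The same section counts readers of the paper chart among those with access.
- Section 4.4.1 has a yes/no item: "Did you look at or discuss the postoperative report card for this patient". Its lead-in is "The following survey questions will be asked of postoperative providers". Section 4.3.3 places the survey QR code on both the print-out and the Epic advisory.

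Section 4.2.1 defines who supplies data: "Included providers are PACU nurses, PACU anesthesiology physicians, wards nurses, and wards midlevel providers". The anesthesia team giving handoff is not listed. Section 4.3.5 (Adherence) says the outcome survey will pick up whether providers think they used the report, and that no further encouragement will be given. On departures it says: "Cross-over into non-contact (failing to contact the correct provider) will be minimized by appropriate training to ACT clinicians".

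**The concern.** A per-protocol set is only as good as the record that defines it, and here none is named. Different readings give very different sets. If handing the print-out to the anesthesia team counts as access, almost nobody is excluded and the analysis nearly repeats the primary one. If only an electronic view counts, every handoff run from paper is dropped.

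The second reading conflicts with the trial's own rationale. Section 1 hypothesizes that "the report card may frame handoff communications around important data and issues relevant to the patient". Suppose the anesthesia team reads the print-out and shapes the handoff around it, while the receiver neither opens nor discusses the card. The intervention has then worked as intended, yet the patient is classed as never accessed. The observation form in the appendix has no item on the card, so it does not fill the hole.

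The exclusion is also one-sided. Section 4.3.5 says cards are not generated for non-contact patients, so nobody can be removed from that group by this rule. If access is related to how the handoff went, the remaining comparison is biased, in either direction. At stake is whether a reader could be misled by the per-protocol result.

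**Working it through.** **1. What each record captures.** No figure in the plan depends on the definition, so the first check is textual.

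| How the card was used | IP log | Survey item | Either record |
|---|---|---|---|
| Receiver opens the electronic card | yes | yes, if they answer | yes |
| Receiver reads the print-out in the chart | no | yes, if they answer | yes, if they answer |
| Giver discusses the card with the receiver | no | yes, if they answer | yes, if they answer |
| Giver uses the paper; no receiver sees or discusses the card | no | no | no |

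The survey item does not depend on format and includes discussion, so it is a partial record of paper use. Non-response matters less than it seems. The primary outcome comes from the same survey, so a patient with no response at all has no handoff rating to analyse. What remains is the last row, plus patients rated by one receiver when only a non-responding receiver used the paper.

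**2. Loss of numbers through missed use (assumed rates).** The documents give no rate of use or of missed use. Take the 100 with-intervention and 50 without-intervention patients of section 4.5. Let u be the share whose card was used and m the share of those uses that the record misses.

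- Users wrongly dropped = 100 × u × m. For u = 0.5, m = 0.25: 12.5. For u = 0.8, m = 0.75: 60.
- Patients kept = 100 × u × (1 − m). For u = 0.5, m = 0.75: 12.5. For u = 0.8, m = 0.25: 60.
- Power for 70% against 88% (two-sided 5%, pooled variance, 50 controls): 20% with 12.5 kept and 65% with 60 kept. With no use missed it is 60% (50 kept) to 71% (80 kept).

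The cost is precision in an analysis for which the plan sets no power target.

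**3. How far one-sided exclusion can shift the rate.** Take 70% acceptable in both groups (the baseline in section 4.5), no true effect, and a share x of with-intervention patients excluded. The retained rate lies between (0.70 − x)/(1 − x) and min(1, 0.70/(1 − x)).

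| x | Lowest | Highest | Shift in points |
|---|---|---|---|
| 5% | 0.65/0.95 = 0.684 | 0.70/0.95 = 0.737 | -1.6 to +3.7 |
| 10% | 0.60/0.90 = 0.667 | 0.70/0.90 = 0.778 | -3.3 to +7.8 |
| 20% | 0.50/0.80 = 0.625 | 0.70/0.80 = 0.875 | -7.5 to +17.5 |
| 30% | 0.40/0.70 = 0.571 | 1.000 | -12.9 to +30.0 |

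The upper limit reaches the 18-point change of section 4.5 at x = 1 − 0.70/0.88 = 20.5%. These are extremes: all excluded patients acceptable, or as many as possible unacceptable.

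**4. Less extreme cases (assumed access rates).** Let a and b be access among acceptable and unacceptable handoffs. The retained share is r = 0.7a + 0.3b and the retained rate is 0.7a/r. Section 4.2.2 plans 350 patients over 30 and 60 days. Split by days, that is 350 × 30/90 ≈ 117 against 233, taking one outcome per patient. Rejection is the exact probability for an uncorrected two-sided 5% chi-square test.

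| a, b | r | Retained rate | Shift in points | Rejection, 117 v retained part of 233 | Rejection, 50 v retained part of 100 |
|---|---|---|---|---|---|
| 0.95, 0.90 | 0.935 | 0.711 | +1.1 | 6% | 5% |
| 0.7, 0.6 | 0.670 | 0.731 | +3.1 | 9% | 7% |
| 0.6, 0.7 | 0.630 | 0.667 | -3.3 | 9% | 7% |
| 0.7, 0.4 | 0.610 | 0.803 | +10.3 | 48% | 23% |
| 0.4, 0.7 | 0.490 | 0.571 | -12.9 | 52% | 27% |
| 0.7, 0.7 | 0.700 | 0.700 | 0 | 5% | 5% |

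**5. What steps 3 and 4 measure.** Nothing in them refers to paper or to a missing definition. The same numbers arise if access is recorded perfectly. They describe any exclusion on something that happens after allocation, and naming the record would not remove them.

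**The case for a change.** The strongest case for a change is that the investigators have committed to reporting this analysis, its membership varies widely with the reading, and paper delivery cannot be fully reconstructed later. A few sentences in section 5.3 and one stored print time would settle membership, and the definition would no longer depend on the person who also rates the handoff. It is true that section 5.3 is silent, that an IP log misses paper, and that the handing-over team is not surveyed.

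Two parts do not stand. First, the records are less blind than that case implies. Section 4.3.5 names the survey as the detector of use. The Non-Technical Summary lists the print-out as one way postoperative providers get the card. Section 4.4.2 allows a research assistant to put the survey questions after up to 150 observed handoffs. Second, defining the set by a card printed before the patient leaves the operating room answers a different question. It shows delivery, not access, and would exclude almost no delivered card, so it would nearly repeat the primary analysis. Nor does it measure the departure in section 4.3.5, which is failure to reach the correct provider; a card can print and still not reach that person.

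**Conclusion.** The observation is correct, but no change to the plan is needed. What is missing is operational detail in an analysis labelled exploratory, with no decision tied to it. An analyst can fill it sensibly from what is collected: count a log entry outside the Anesthesia Control Tower or a survey yes as access, and report how many patients were excluded and on which record. The residual error is confined to handoffs where paper was used and no responding receiver saw or discussed the card. Its frequency cannot be derived from the documents.

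The possible distortion is not trivial at the extremes: -7.5 to +17.5 points with 20% excluded. Rejection of about 50% at the planned 350 patients needs an assumed 30-point gap in access between acceptable and unacceptable handoffs; gaps of 5 to 10 points give 6% to 9%. These figures assume 70% acceptable in both groups, no true effect and one outcome per patient. They are a reason to read any per-protocol result here as descriptive, which its exploratory label already signals. A delivery-based set would be a debatable trade rather than a gain. The intention-to-treat comparison is unaffected under every reading.

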#### 4.3.3 Other Interventions

We will notify the PACU anesthesiology resident when report cards are generated for high-risk patients. This notification will occur by SMS to a BJH-issued phone which is passed between residents at each shift. The notification does not contain PHI or PII, only that a particular OR has a high-risk patient.

Discussed in the Outcomes section, the study also includes a survey for providers, which we mention here because of its patient-information security implications. The Epic BPA (and printout) will contain a patient-specific link and QR code to a RedCap survey. This survey contains no PII, only a randomized study ID.

Information flow and security. To minimize the risk of protected health information (PHI) or personally identifiable information (PII) leaking from the health-care environment, we will restrict communications to providers to secure and auditable delivery modes. A diagram of the flow of information is included in Figure 6. There are 3 distinct flows of information: from the ML server and ACT tower to the PACU provider notifying them that a high-risk patient is emerging (the alert), from the ML server and ACT to the healthcare provider in the body of the report card, and between the postoperative provider to the research coordinator with their survey responses (provider survey).

The alert is designed to include minimal potentially sensitive information. It will contain the location of the patient (operating room, PACU bay destination) and that the risk of patient decompensation is elevated. The name, MRN, date of birth, or other identifiers are not included.

The only individuals who can access the report card (which contains no PII) are (1) Epic users who access the patient's chart (2) pre-approved users in the ACT who log in with their wustl-key (3) individuals reading the patient's paper chart. The ML server will be behind the WashU-BJH firewall, and therefore only accessible from authenticated users on campus or logged in via VPN. Access to the report card will be logged by IP address.

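### The exploratory per-protocol analysis can drop patients from with-intervention days only, so provider behaviour after allocation can shift the result in either direction even when the card has no effect

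*Combined protocol and SAP*

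**What the plan says.** Section 5.3 makes intention to treat primary, comparing the with- and without-intervention groups by chi-square. It then adds, labelled as exploratory, "per-protocol analyses in which patients whose report card was never accessed (outside of the ACT) are excluded". It describes no matching restriction on controls, no adjustment for who opens a card, and no order in time between access and the rated handoff.

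Section 4.3.5 says of control patients: "Crossover from non-contact to contact will not occur because report cards are not generated for these patients". On use of the card it says that "no other encouragement to use it will be provided".

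There are two routes to the card. Section 4.3.3 covers the electronic one: "Access to the report card will be logged by IP address". The paper route is in 4.3.1, after the example card: "After manual validation, the report card will print directly in the operating room". Section 5.3 does not say whether reading the paper copy counts as access.

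**The concern.** Read together, 5.3 and 4.3.5 make the exclusion one-sided. On with-intervention days it removes handoffs in which nobody outside the control tower opened the card. The handoffs on control days that would have gone the same way cannot be identified, and all of them stay in. Whatever leads a team to open a card (time, attention, experience, worry about the patient) may also affect how that team rates the handoff, and that self-rating is the primary outcome (4.4.1). A perfect access log would not cure this.

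The missing time order adds to it. The rule works at patient level, while several providers rate successive handoffs (4.2.1 and section 1). A ward provider who opens the card later keeps the patient in the analysis of an earlier PACU handoff. The survey link is itself in the Epic advisory and on the print-out (4.3.3), so opening the advisory to fill in the survey could count as access.

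At stake is the reading of a secondary result: a difference produced by selection could be taken as the effect of the card when it is used.

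**Working it through.** **Inputs from the documents.** 70% acceptable at baseline, 50 patients without and 100 with intervention, 18-point detectable increase at 80% power (4.5); 350 evaluation patients over 30 control and 60 intervention days (4.2.2). If patients spread evenly over days, that is 350 × 30/90 ≈ 117 and 350 × 60/90 ≈ 233.

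**Assumed, because the documents are silent.** Access share a of 40% to 80%; gap g in acceptable handoffs between accessed and unaccessed patients; two-sided 0.05 test without continuity correction; independent patients; no effect of the card.

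**The plan's own figure.** The plan gives no figure for this analysis. The 18 points in 4.5 serve here only as a yardstick. Recomputed with pooled variance, the detectable difference for 50 against 100 is 18.9 points two-sided and 17.2 one-sided. Nothing below depends on which is meant.

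**Formula.** With no card effect the overall rate is 70% on both day types:

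- a × pA + (1 − a) × pN = 0.70, with pA − pN = g
- hence pA = 0.70 + (1 − a) × g
- per-protocol difference = pA − 0.70 = (1 − a) × g

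Check at a = 0.4, g = 0.30: pA = 0.88, pN = 0.58, and 0.4 × 0.88 + 0.6 × 0.58 = 0.70. The difference is +18 points.

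**Results.** The last two columns give the probability of a significant result in favour of the card when it does nothing, by exact enumeration. The ranges run from 80% down to 40% access.

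| Gap g | Spurious difference | 50 controls vs 100 × a | 117 controls vs 233 × a |
|---|---|---|---|
| 0 | 0 | about 2.5% | about 2.5% |
| +10 points | +2 to +6 | 5% to 9% | 6% to 16% |
| +20 points | +4 to +12 | 8% to 25% | 12% to 52% |
| +30 points | +6 to +18 | 12% to 55% | 21% to 90% |

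Under intention to treat with no card effect, the same probability is about 2.6%.

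**Reversed gap.** If g = −20 points, the difference is 0.2 × (−20) = −4 points at 80% access and 0.5 × (−20) = −10 points at 50%.

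**An estimate that keeps everyone.** The with-minus-without difference divided by a is (0.70 − 0.70)/a = 0 in every row. This follows by construction: selection cannot enter because nobody is dropped. The price is precision. With a treated as known, the interval is 1/a times the intention-to-treat interval: 1.25 times at 80% access and 2.5 times at 40%.

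**The case against.** **The plan already calls the analysis exploratory and makes intention to treat primary.** This stands, and it limits the weight of the point. A reader might infer that the trial's main conclusion is compromised; it is not, because the primary comparison drops nobody on access. The label does not, however, tell a reader that the two groups are selected differently.

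**The direction is unknown.** This also stands. A reader might infer that the analysis is tilted towards the card because attentive teams open it. The documents do not show that. Section 1 describes the card as drawing attention to high-risk patients, and 4.3.1 expects providers to look into higher-risk cases before arrival, so cards may be opened more often where handoffs are harder. An attentive receiver may also be quicker to say that information was missing.

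**Non-access may reflect failed delivery rather than inattention.** This is possible. The print-out goes to the anesthesia team for handoff, the PACU resident gets a text message, and 4.3.5 itself mentions failure to contact the right provider. That changes the likely size of g, not the one-sidedness.

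**The scaled estimate has its own strained assumption.** It requires that the intervention does nothing when the card is not used. The text message (4.3.3) and the print-out in the giving team's hands (4.3.1) could each change a handoff without the receiver opening anything. This stands and must be stated with the estimate. The estimate still keeps one property that the exclusion lacks: it is centred on zero when the intervention as a whole has no effect.

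**The data may not be complete.** Paper reading is not described as logged, and no handoff time is described as recorded. So the requirement that use come first can be applied only where times allow.

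**Conclusion.** The point holds, with modest weight. The exclusion is one-sided as a matter of the plan's own text, and the resulting contrast does not estimate what the card does when used. With no card effect the bias is (1 − a) × g. Positive gaps of 10 to 30 points give about +2 to +18 points, the top of which equals the planning difference in 4.5; a zero gap gives no bias and a negative gap gives a bias against the card. These sizes rest wholly on assumed access shares and gaps, so they show what could happen and do not predict it. Days alternate and are not randomized, a limit that the intention-to-treat and scaled estimates share.

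**What to change.** In 5.3, replace the exclusion with an exploratory as-used estimate that keeps all patients: the with-minus-without difference in acceptable handoffs, divided by the proportion of with-intervention patients whose card was used, with an interval that clusters by day.

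- Define use from the 4.4.1 survey item on looking at or discussing the card, the access log, or both, and say how paper reading counts. Count only use before or at the rated handoff where times allow.
- State the assumption that neither the text message nor the print-out has an effect when the card is not used. If they improve handoffs on their own, the estimate is an upper-end figure for use of the card.
- State that the interval is wider than the intention-to-treat one, and that the estimate becomes unstable if few cards are used.
- If the exclusion analysis is still reported, give the analysis set for each group and say that it is open to selection bias in either direction and is not evidence of benefit.

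The cost is a change of wording and some analysis code. No additional patients are needed. Applying the time order fully would need handoff and access times, which the documents do not say are both recorded.
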